### **6.2 Efficacy Analysis**

### 6.2.1 Primary Efficacy Analysis

#### 6.2.1.1 Modified Ashworth Score

The first and best known scale for measuring the degree of spasticity was the Ashworth scale, first developed in 1964 for use in a multiple sclerosis therapeutic trial. Spasticity accounts for much of the disability affecting lower limbs. Modified Ashworth score for the 12 movements of the lower extremities that will be measured will be evaluated as one of the primary efficacy parameters. The Ashworth assessment is the current standard for clinical assessment of lower extremity spasticity and the most commonly used tool to evaluate the efficacy of pharmacologic and rehabilitation interventions for treatment of spasticity.

The 6-point modified Ashworth scale scores are presented below:

Score	:	Analysis Val	u e	: Degree of Muscle Tone
0	:	0	:	No increase in tone
1	:	1	:	Slight increase in muscle tone, manifested by a catch, followed by minimal resistance at the end of the range of movement
1+	:	2	:	when the affected part(s) is moved in flexion or extension Slight increase in muscle tone, manifested by a catch, followed by minimal resistance throughout the remainder
2	:	3	:	(less than half) of the range of movement  More marked increase in muscle tone through most of the
3	:	4 5		range of movement, but affected part(s) easily moved Considerable increase in muscle tone, passive movement difficult Affected part(s) rigid in flexion or extension

\*note: A change from 1 to 1+ and from 1+ to 2 will each be counted as a 1-point change

For the purposes of summaries and analyses, the analysis value above will be presented.

#### 6.2.1.2 Clinical Global Impressions of Change (CGIC)

Version 9.0

CGIC will be assessed at Visits 4, 7, 8, 9, 10, and 11.

The 7-point scale for CGIC is presented below:

**Scale**: Overall impression

**0** : Not assessed

1 : Very much improved2 : Much improved3 : Minimally improved

4 : No change

5 : Minimally worse6 : Much worse7 : Very much worse

#### 6.2.1.3 Derivation of Primary Endpoint

The primary efficacy variable is the proportion of subjects who become a Treatment Failure during the double-blind randomized withdrawal part (Part 3). Using the primary efficacy variable, the CRO will perform a determination of failures (the blinded failure analysis). A subject's response status will be determined after database lock, but prior to unblinding the data. A subject who meets the following criterion will be considered a treatment failure:

• A CGIC of ≥ 5 ("minimally worse" to "very much worse") and at least one movement with a ≥ 1 unit increase in MAS from Baseline (A change from 1 to 1+ and 1+ to 2 will be counted as a 1-unit change)

The MAS at a given visit will be	e recorded for each of the	12 movements measured.	

For the Treatment Failure analysis, subjects who provide MAS and CGIC scores at Visit 11 and meet the treatment failure criterion at Visit 11,

21Sep2017

All other subjects will be classified as not being Treatment Failures.

#### 6.2.1.4 Null Hypothesis of the Primary Effiacy Analysis

The null hypothesis is that there is no difference in the failure rates between groups. The alternative hypothesis is that there is a difference in the failure rates between the groups.

### 6.2.1.5 Primary Efficacy Analysis

The primary efficacy analysis will be performed using the intent-to-treat (ITT) population.

The primary efficacy analysis will be carried out using a two-sided test at the alpha=0.05 level of significance.

. Alternate approaches to handling missing data are discussed in Section 6.2.1.6.

### 6.2.1.6 Sensitivity Analysis of the Primary Efficacy Analysis

Several sensitivity analyses of the impact of missing data on the primary efficacy endpoint will be performed. First, the primary efficacy analysis will be repeated in the PP population if it differs in size from the ITT population by more than 10% overall. In addition, the primary efficacy analysis will also be performed (using the ITT population) with different assumptions regarding the response status of a subject with missing data.

### 6.2.2 Secondary Efficacy Analyses

#### 6.2.2.1 Subject Global Impression of Severity (SGIS)

Statistical Analysis Plan Version 9.0 21Sep2017

Subjects will be asked to rate their overall impression of severity at Visits 4, 7, 8, 9, 10, and 11. At each of these visits, the subject is to be asked "Overall, how would you rate the severity of your spasticity over the past week?"

The 7-point scale for SGIS is presented below:

[figure not shown]
Scale	:	Overall impression
0	:	Not assessed

Normal, no spasticity
 Borderline spasticity
 Mild spasticity
 Moderate spasticity

5 : Marked spasticity 6 : Severe spasticity

7 : Worst spasticity imaginable

#### 6.2.2.2 Secondary Analysis of SGIS

If Visit 11 is missing, the last available SGIS will be used.

### 6.2.3 Additional Efficacy Analyses

[figure not shown]
Page 33 of 53

## 6.2.4.5 Time Since Last Dose

Because the timing of post-dose of assessments is a factor potentially related to efficacy, time from prior dose to modified Ashworth assessment will be summarized descriptively for each visit in Part 3 (Visits 8, 9, 10, 11), by treatment group.

#### **Subgroup Analyses** 6.2.4.6

## **6.3 Safety Analysis**

#### 6.3.1 Adverse Events

All adverse events will be coded using version 15.0 of MedDRA, which will be noted in the CSR.

Adverse events reported as pre-existing at the start of the run-in emerge during the treatment phase will be considered pre-treatment adverse events; these will be flagged in a listing.

A treatment-emergent adverse experience (TEAE) is defined as any event that only occurred after administration or that existed before drug administration but increased in severity or treatment attribution.

The duration of an AE will be calculated as:

$$Duration = (AE End Date - AE Onset Date) + 1$$

When AE start and/or stop dates are missing, the following imputations will be made (subject to medical review):

- Missing AE Start Dates
- 1. If onset date is completely missing, then onset date is set to date of first dose
- 2. If year is present and (month and day are missing), or (month is missing but day is present):
  - a. If year = year of first dose, then set date to first dose date
  - b. If year < year of first dose and medication stop month and year are available, then set to first of the end month
  - c. Otherwise if year < year of first dose, then set month and day to December 31st.
  - d. If year > year of first dose, then set month and day to January 1st.
- 3. If month and year are present and day is missing:
  - a. If year=year of first dose and

- i. If month = month of first dose then set day to day of first dose date
- ii. If month < month of first dose then set day to last day of month
- iii. If month > month of first dose then set day to first day of month
- b. If year < year of first dose then set day to last day of month
- c. If year > year of first dose then set day to first day of month
- 4. If the AE start date is completely missing and the corresponding stop date is completely missing, the AE start date will remain missing.

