#### 10.4.5.1 Adverse Events

All treatment-emergent adverse events (TEAE) will be coded in a standardized manner for regulatory activities. TEAEs will be coded according to body systems and preferred terms. A

Confidential Page 59 of 67

 
TEAE is defined as any event that only occurred after administration or that existed before drug administration but increased in severity or treatment attribution. For the randomized withdrawal phase, emergent events will be determined relative to the double-blind medication.
Adverse events reported as pre-existing at the start of the run-in or that emerge during the treatment phase will be considered pre-treatment adverse events. These will be summarized separately.
The incidence of TEAEs and SAEs will be summarized for the s (Part 2) and also by treatment group during the double-blind, par (Part 3). For each part, the incidence of TEAEs will be presented by system organ classification and preferred terms according to the Medical Dictionary for Regulatory Activities (MedDRA®), by causality, by severity, and by action taken. In addition, separate summaries will be prepared with subjects categorized by sex, age (below 65 years of age and 65 years of age and older), and race.
The effects of concomitant medications and/or medical conditions present at screening will also be explored. Should any medications be used by or conditions be present in 20% or more of the subjects overall, subjects will be categorized accordingly and the incidence of TEAEs in each par summarized. Additional drugs or diagnoses of interest may be identified during the blinded data review.
In addition, adverse events will be listed for all subjects, including verbatim and coded terms.
10.4.5.2

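### AE onset imputation ignores a known stop date, giving non-positive durations and false TEAEs; if first dose means the open-label dose, it can also date Part 3 events to Part 2

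*SAP*

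**What the plan says.** SAP 6.3.1 lists rules for adverse events (AEs) with an incomplete start date, with a general proviso for medical review.

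- Rule 1: "If onset date is completely missing, then onset date is set to date of first dose".
- Rule 2a (month missing): "If year = year of first dose, then set date to first dose date".
- Rule 2b: "If year < year of first dose and medication stop month and year are available, then set to first of the end month". This is the only rule that takes a value from a stop date. It speaks of a medication stop, as the parallel list in SAP 6.1.7 does.
- Rule 2d (month missing, later year): 1 January of that year.
- Rule 3a applies when only the day is missing and the year is that of first dose. Its case (i) reads "If month = month of first dose then set day to day of first dose date". Case (ii) puts an onset in any earlier month on the final day of that month. For an onset in a later month, case (iii) reads "If month > month of first dose then set day to first day of month". Rules 3b and 3c treat an earlier or later year in the same way as (ii) and (iii).
- Rule 4 leaves the start missing only when start and stop are both completely missing.

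Duration is defined as "Duration = (AE End Date - AE Onset Date) + 1". For Part 3, Protocol 10.4.5.1 states that "emergent events will be determined relative to the double-blind medication". SAP 9.1 plans separate tables of treatment-emergent AEs (TEAEs) for Part 2 and, by arm, for Part 3. The visible text of SAP 6.3.1 does not define first dose, and its date rules mention neither Visit 7 nor the first double-blind dose.

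**The concern.** Setting an unknown onset to first dose is a usual and cautious choice when the stop date is unknown or falls after first dose, because an ambiguous event is then counted. It goes wrong when the stop date already shows that the event was over. Rule 4 sharpens the problem: rule 1 acts only when some stop information exists, and then ignores it. Such events can occur, since Protocol 9.1.1 has subjects asked about adverse experiences before dosing and Protocol Table 1 schedules AE assessment from Screening.

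Two things are at stake. Part 2 TEAE counts could include events that cannot be treatment-emergent. And Part 3 is the only randomized safety comparison: if its partly dated events are dated to Part 2, they leave the by-arm tables. SAP 6.3.1 also tabulates TEAEs by dose at earliest onset, so a wrong onset can attach an event to the wrong dose.

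**Working it through.** **Inputs.** Screening opens at most 14 days before Visit 1 (SAP 3.2). Visit 2 is Day 8, Visit 7 Day 120 and Visit 11 Day 148 (SAP Table 1). Schedule check: (120 - 8)/7 = 16 weeks, which matches the stated length of Part 2. Part 3 lasts 148 - 120 = 28 days.

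**Assumptions.** First dose is at Visit 2, where SAP 4.6.1 starts its day count (repeated below with Visit 1). An onset on the first-dose date counts as treatment-emergent. Each event goes to the part in which its imputed onset falls. The rules run as written, with no correction at medical review.

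**Worked subject.** Visit 1 on 09-Mar-2015 gives screening from 23-Feb, Visit 2 on 16-Mar, Visit 7 on 06-Jul and Visit 11 on 03-Aug.

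| Event | Rule | Onset assigned | Duration (days) | Placed in |
|---|---|---|---|---|
| Stop 06-Mar; onset missing, or 2015 only, or Mar-2015 | 1, 2a, 3a(i) | 16-Mar | -10 + 1 = -9 | Part 2, false TEAE |
| Stop 26-Feb; onset Feb-2015 | 3a(ii) | 28-Feb | -2 + 1 = -1 | Pre-treatment |
| Began in Part 3, stop 21-Jul; onset missing, or 2015 only | 1, 2a | 16-Mar | 127 + 1 = 128 | Part 2 |
| Began in Part 3, stop 21-Jul; onset Jul-2015 | 3a(iii) | 01-Jul | 20 + 1 = 21 | Part 2 |

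**Why the first row is general.** Let F be the first-dose date and S the stop date. Rules 1, 2a and 3a(i) set onset to F. If S < F, duration is S - F + 1, which is at most 0 (exactly 0 when S is the day before F). Every pre-dose event under these rules is therefore affected. Rules 3a(iii) and 3c assign the first of the true onset month, which cannot be later than the true onset or a fully recorded stop, so they never give a non-positive duration.

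**Enumeration.** The rules were applied for every Visit 1 date in 2015, every onset/stop pair between the start of screening and first dose, and every Part 3 onset from Day 120 to Day 148, all equally weighted. Ranges cover first dose at Visit 2 and at Visit 1.

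| Rule | Ended before first dose: duration 0 or less | Ended before first dose: false TEAE | Part 3 event dated to Part 2 |
|---|---|---|---|
| 1, 2a | 100% | 100% | 100% |
| 3a(i) | 100% | 100% | does not arise |
| 3a(ii), 3b | 45-47% | 0% | does not arise |
| 2d | does not arise | does not arise | 88-89% |
| 3a(iii) | does not arise | does not arise | 53-54% |
| 3c | does not arise | does not arise | 46-47% |

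Across all Part 3 events lacking only the day, 51% are dated to Part 2.

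**Hand check of the 51%.** Put Visit 7 on day d of a 30-day month, with onset uniform over 28 days. An event is misplaced if it starts in the same month as Visit 7 and d > 1. The share is 0 for d = 1, 1 for d = 2 and d = 3, and (31 - d)/28 for d = 4 to 30. The last group sums to (27 x 28/2)/28 = 13.5. The average is (2 + 13.5)/30 = 0.517.

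All these percentages are conditional on the start date being partial or missing.

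**The case against.** **Safeguards.** The rules are open to medical review, missing values are queried (Protocol 10.7, SAP 5.3), and all data are source-verified (Protocol 11.4). These steps make partial dates rarer. They do not bound an imputed date, and the review proviso has no criteria.

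**Pre-existing events.** Protocol 10.4.5.1 and SAP 6.3.1 class events reported as pre-existing at the start of the run-in as pre-treatment. Events reported that way may escape the TEAE count. But the visible text does not say that this classification overrides an imputed date, and the impossible duration remains either way.

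**Little visible effect.** No planned table title in SAP 9.1 names AE duration. The rules are the same in both arms, and the primary endpoint is untouched. All of this stands.

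**Part 3.** A reader might infer that the SAP definitely moves Part 3 events into Part 2. The documents do not support that without a condition. SAP 4.6.1 and the prior-medication definition in SAP 6.1.7 point to the start of Part 2, but SAP 6.3.1 is partly redacted and its visible text does not define first dose. Protocol 10.4.5.1 measures Part 3 emergence against double-blind medication, and nothing visible in the SAP contradicts it. If first dose is part-specific, this limb falls away, although partly dated Part 2 events could then move into Part 3.

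**Medications.** Because SAP 6.1.7 uses the same list, a reader might infer that a prior drug becomes concomitant. It does not. That section defines a prior medication by its being discontinued before first dose, so a recorded earlier stop keeps it prior whatever start is imputed.

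**Conclusion.** The stop-date error holds on the visible text, whether first dose is at Visit 1 or Visit 2. Rules 1, 2a and 3a(i) give every AE that ended before first dose a duration of 0 or less and date it as treatment-emergent. Rules 3a(ii) and 3b give a non-positive duration in a little under half of such cases and never a false TEAE.

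The Part 3 misplacement is conditional on first dose being the open-label first dose. On that reading it affects all Part 3 events under rules 1 and 2a, most under rule 2d, and about half of those lacking only the day (rules 3a(iii) and 3c).

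The documents do not say how many AE dates are partial, so no count of affected events can be given. The overall effect is probably small and confined to safety summaries. The point is still worth correcting, because a stated rule produces impossible records and the remedy is cheap.

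**What to change.** Amend SAP 6.3.1 before unblinding.

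1. If the recorded (or imputed) stop date is earlier than the onset date that the rule assigns, set onset to the stop date. In the worked case onset becomes 06-Mar-2015, duration 1 day, and the event stays pre-treatment.
2. State which first dose the rules refer to, if redacted text does not already do so. For AEs first reported after Visit 7 whose partial onset and stop dates do not exclude Part 3, impute the later of the rule's date and the first double-blind dose date. AEs already reported at or before Visit 7 stay in the open-label period. In the worked case, an event first reported after Visit 7 with onset Jul-2015 and stop 21-Jul-2015 gets onset 06-Jul-2015, duration 15 + 1 = 16 days, and is counted in Part 3.

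The limit to events first reported after Visit 7 matters. Without it, an ongoing event reported at Visit 3 with only the year known could be moved into the randomized tables.

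The cost is a few sentences and minor programming. The AE items listed in Protocol 9.2.1 do not include the visit of first report, so the program needs it from the visit-level AE assessments; I assume that it can be obtained. A few ambiguous late Part 2 events may be counted in Part 3. The rule is the same in both arms, but such events could slightly dilute a between-arm difference. SAP 6.1.7 needs no change on this ground.

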#### • Missing AE Stop Dates

If the stop date is completely missing and the event is not ongoing (i.e., an outcome is indicated), the stop day will not be estimated.

If only the day of resolution is unknown, the day will be assumed to the last of the month (e.g. ??-JAN-2011 will be treated as 31-JAN-2011)

If the stop date is completely missing and the event is ongoing, the event will be noted as "Ongoing" in the stop date column in the AE listings.

The incidence of TEAEs and serious adverse events (SAEs) will be summarized

An overall summary of TEAEs will include:

- o Incidence of subjects with one or more TEAE
- o Incidence of TEAEs by highest relationship
- o Incidence of TEAEs by highest severity
- o Incidence of TEAEs by action taken
- o Incidence of TEAEs by outcome
- o Incidence of treatment-emergent SAEs

The incidence of TEAEs will be presented by system organ classification and preferred terms, by highest relationship, by treatment-related status (possibly, probably, certainly), by highest severity, by descending order of frequency of preferred terms, by dose at earliest onset for all possible dose groups, and by discontinuation status.

In addition, separate summaries of TEAEs will be prepared with subjects categorized by sex, age (below 65 years of age and 65 years of age and older), race, and renal impairment category (see Section 6.1.2).

The effects of concomitant medications and/or medical conditions present at screening will also be explored. Should any medications be used by or conditions be present in 20% or more of the subjects overall, subjects will be categorized accordingly and the incidence of TEAEs in each part summarized. Additional drugs or diagnoses of interest may be identified during the blinded data review.

The incidence of treatment-emergent serious adverse events (SAEs) will be presented by system organ classification and preferred terms, by treatment-related status (possibly, probably, certainly), and for those that are fatal.

Adverse events will be listed for all subjects, including verbatim and coded terms.

